# **11.2** Calculation or derivation of safety variable(s)

The following safety data will be collected: AEs, haematology, clinical chemistry, urinalysis, vital signs, 12-lead ECG, physical examination. Change from baseline (Visit 2) to end of treatment will be calculated for relevant measurements.

All AEs will be analysed in terms of descriptive statistics and qualitative analysis. AEs will be listed for each patient and summarised by System Organ Class and preferred term by using MedDRA. Laboratory safety assessments and vital sign data outside the AstraZeneca extended reference ranges will be highlighted.

### 11.2.1 Other significant adverse events (OAE)

During the evaluation of the AE data, an AstraZeneca medically qualified expert will review the list of AEs that were not reported as SAEs and DAEs. Based on the expert's judgement, significant adverse events of particular clinical importance may, after consultation with the Global Patient Safety Physician, be considered OAEs and reported as such in the Clinical Study Report. A similar review of laboratory/vital signs/ECG data will be performed for identification of OAEs.

Examples of these are marked haematological and other laboratory abnormalities, and certain events that lead to intervention (other than those already classified as serious), dose reduction or significant additional treatment.

# **11.3** Calculation or derivation of patient reported outcome variables

Outcome variables for other diary card variables (EXACT, BCSS) will be computed in a similar manner to efficacy diary card variables (PEF,  $FEV_1$  and use of reliever medication). In addition to this a total score for BCSS and EXACT, separately, will be computed and will serve as the main outcome variable for such data. The entire EXACT tool will be used to assess COPD exacerbations in addition to the per protocol analysis. However, a select number of items from the EXACT tool will be used to assess symptoms of COPD.

For SGRQ-C measured at the clinic, an overall score will be computed on each of the 3 different domains (symptoms, activity and impact) and a total score will be computed according to the rules defined by the questionnaire.

# **11.4** Calculation or derivation of pharmacokinetic variables (not applicable)

# **11.5** Calculation or derivation of pharmacodynamic variable(s)

Markers of tissue degradation (urine desmosine) levels from Visits 2 to 6 will be evaluated. Urine desmosine will be normalised for creatinine.

## 11.6 Calculation or derivation of pharmacogenetic variables

Please refer to Appendix D.

# 11.7 Calculation or derivation of health economic variables (not applicable)

# 12. STATISTICAL METHODS AND SAMPLE SIZE DETERMINATION BY ASTRAZENECA

### **12.1** Description of analysis sets

### 12.1.1 Efficacy analysis set

There will be 1 efficacy analysis set based on the 'full analysis set', as defined in the international conference of harmonization E9 guideline. This means that all patients who receive at least 1 dose of investigational product (AZD9668 or placebo) and for whom post-dose efficacy data are available will be included in the efficacy analysis set.

### 12.1.2 Safety analysis set

All patients who received at least 1 dose of randomised investigational product (AZD9668 or placebo) and for whom any post-dose data are available will be included in the safety analysis set.

## **12.2** Methods of statistical analyses

AWT-Pi10 will be the primary variable. The outcome variables from the MSCT will be compared between AZD9668 and placebo using an Analysis of Variance (ANOVA) model with fixed factors treatment and country and using baseline as a covariate. A 90% confidence interval will be constructed for the treatment difference and p values given. If appropriate, data will be log-transformed before analysis.

Plots of MSCT variables vs clinic lung function variables will be produced. In addition, the correlation of MSCT variables with the clinic lung function variables may be assessed.

Analysis of clinic lung function data (spirometry, body plethysmography and  $DL_{CO}$ ), diary data and PROs will be analysed using an ANOVA model in a similar manner to the MSCT variables.

Mean value plots of effect versus time will be produced for most variables. These mean values are to be computed using the principle of last value carried forward, so that the number of patients are the same on each assessment time. For variables obtained at the clinic, the time scale will be visit number, for diary data it will be days since randomisation.

Analysis of exacerbations may be done, if there are a sufficient number to make such an analysis meaningful. If so, the time to first clinic identified COPD exacerbation will be analysed using a Cox proportional hazards model. Further analyses may be performed. The movement of the EXACT will be explored in relation to the clinic defined exacerbations. The movement of some of the items on the EXACT will be explored to assess the symptoms of COPD.

Adverse events will be analysed by means of descriptive statistics and qualitative analysis. Adverse Events will be listed for each patient and summarised by System Organ Class and preferred term assigned to event by using Medical Dictionary for Regulatory Activities (MedDRA).

Concomitant medications will be classified according to the AstraZeneca Drug Dictionary, the Anatomical Therapeutic Chemical Classification (ATC) system and the Committee for Proprietary Medicinal Products (CPMP) route of administration dictionary. All concomitant medications reported at entry and recorded during the study will be listed.

# **12.3** Determination of sample size

This study is a feasibility study and as such the sample size in this study has not been based on obtaining power to detect specific effects. There is not adequate data to do such a powering. The sample size is 25 patients in each arm. This number has been considered sufficient to detect clinically relevant effects on AWT-Pi10. Assuming the effect size is at least 0.5 (ie, the standard deviation is not more than twice that of the treatment difference observed), we will have at least 80% power to demonstrate an effect at the 5% significance level with a 1-sided test. The sample size for this study was selected to be consistent with the research hypothesis as described in Section 1.2. The sample size is based on similar studies in asthmatics where anti-inflammatory treatments have shown a treatment effect in 12 weeks (Capraz F et al 2007, Niimi A et al 2004) and has been kept low to ensure minimal radiation exposure for a feasibility study

The number of patients that will agree to participate in the genetic research is unknown. It is therefore not possible to establish whether sufficient data will be collected to allow a formal statistical evaluation or whether only descriptive statistics will be generated. A statistical analysis plan will be prepared where appropriate.

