The total radiation dose for the study is expected to be around 10 - 12 mSv. This dose is close to accepted radiation dose for biological research (1 to 10 mSev). In the present study the radiosensitive group has been therefore excluded to a major extent. The older demographic of patients fall into a low risk profile for risk of radiation, and the laboratory safety results from Visit 1b must be reviewed and considered eligible prior to baseline scan to avoid any unnecessary radiation exposure. The selection of patients includes male and female patients aged 50 - 80 years. Each patient will receive 4 scans, 2 scans (a paired inspiratory and expiratory scan) at each visit, 3 months apart. The imaging protocol and study design is based on the EU guidance (See Guidance document). The potential benefits of the study are expected to be Category IIB (aimed directly at the diagnosis, cure or prevention of disease). Since this is a study to establish the feasibility of a clinical trial in COPD evaluated by MSCT the study has not been adequately powered to demonstrate efficacy but only to detect a trend.

The study design chosen for this study is considered to optimal to detect a clinically meaningful effect of AZD9668 while the safety risks are minimised. The benefit/risk balance of using AZD9668 in the present study in patients with COPD can therefore be considered acceptable.

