# 3.1 Overall study design and flow chart

This is a 12-week randomised, double-blind, placebo-controlled, parallel-group, multi-centre phase IIb study to assess the effect of AZD9668 on structural changes in the airways in COPD patients. The primary variable is AWT-Pi10 assessed by MSCT.

The plan is to enrol approximately 70 patients, men and women aged 50 to 80 years inclusive, to obtain approximately 50 randomised patients. Approximately 15 centres in Canada and Europe are planned to participate in the study with 3 to 10 patients per centre.

There will be 8 visits to the clinic: Visit 1a (enrolment), Visit 1b (screening), Visit 2 (randomisation), Visits 3, 4, 5 and 6 (after 1, 4, 8 and 12 weeks of treatment) and Visit 7 (follow-up).

All inclusion/exclusion criteria that can be assessed at each visit should be checked carefully, including patients suitability to use electronic devices/perform home spirometry, before therapy is changed and before randomisation.

At Visit 1a all patients will be informed about the study and, if willing to take part in the study, sign the informed consent form and have demographic data collected. Signing the informed consent form must be done before any study-related procedures, restrictions or screening assessments are performed. The timing of this visit in relation to Visit 1b will be dependent on the medication being taken by the patient on entry to the study as described in Section 5.5.3.2.

At Visit 1b, all patients must be on tiotropium alone as maintenance therapy. In addition to tiotropium maintenance therapy, patients will be allowed to use short-acting  $\beta_2$ -agonists (SABA) as reliever medication throughout the study. See Section 5.5.3.2 regarding provision of tiotropium and SABA.

At Visit 1b, patients will be screened and evaluated for eligibility to enter the 14-17 day run-in period. Included patients must have a documented COPD history with symptoms for at least 1 year according to GOLD 2008, and they must be ex-smokers with a smoking history of at least 10 pack years. Their FEV1 must be 40 - 70% of the predicted normal value and FEV1/FVC <70%, both values post-bronchodilator.

Included patients will be asked to fill in an electronic diary and to measure  $FEV_1$  and PEF morning and evening from Visits 1b to 6.

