# 5.2 Patient enrolment and randomisation

The Principal Investigator will:

- 1. Obtain signed informed consent from the patient before any study specific procedures are performed.
- 2. Assign the patient a unique enrolment number, beginning with "E0001001 (EXXXXYYY)" where XXXX reflects the centre number and YYY will be allocated sequentially to enrolled patients at each centre
- 3. Determine patient eligibility. See Sections 4.1, 4.2 and 4.3.
- 4. Assign eligible patient unique randomisation code (patient number) at Visit 2.

Re-enrolment is allowed only if enrolment has failed due to technical problems, eg, with the eDiary. Patients failing to meet an inclusion or meeting an exclusion criterion must not re-enter the study. If a patient discontinue the study after randomisation he/she can not re-enter the study.

If a patient withdraws from participation in the study, then his/her enrolment/randomisation code cannot be reused. Patients who discontinue the study after randomisation will not be replaced.

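### The stated power of at least 80% is wrong: 25 patients per arm, effect size 0.5 and a 1-sided 5% test give about 54%

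*Protocol*

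**What the plan says.** Protocol Section 12.3 supplies every input for a power calculation:

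- Size: "The sample size is 25 patients in each arm". Section 3.1 agrees, with enrolment planned "to obtain approximately 50 randomised patients".
- Effect: "Assuming the effect size is at least 0.5 (ie, the standard deviation is not more than twice that of the treatment difference observed").
- Test and result: "we will have at least 80% power to demonstrate an effect at the 5% significance level with a 1-sided test".

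Section 12.2 sets the comparison for AWT-Pi10 and the other CT variables: AZD9668 against placebo, in a model with treatment and country as factors and baseline as covariate, with a 90% confidence interval. That interval matches a 1-sided 5% test.

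Two other statements point the opposite way. Section 12.3 opens by saying that this is a feasibility study, that its size was not derived from power, and that the data for such a calculation are lacking. Section 1.4 says that "the study has not been adequately powered to demonstrate efficacy but only to detect a trend". Section 12.3 nevertheless also judges the number sufficient to detect clinically relevant effects on AWT-Pi10.

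**The concern.** Twenty-five per arm is small for a standardised difference of 0.5 between two independent groups, and 80% power there looks too high even with a 1-sided 5% test. The claim concerns the primary variable.

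Anyone who takes it at face value will think that a non-significant AWT-Pi10 result has at most a one-in-five chance of hiding a real 0.5 SD effect. Section 1.3 says the findings, together with those of two large parallel Phase IIb trials, will be used to design longer and larger imaging studies in Phase III. An overstated power makes a null result look more informative than it is. Section 1.4 also weighs a radiation dose of about 10 to 12 mSv against what the study can show, and that judgement should rest on the correct chance of detecting an effect.

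The wording adds a smaller problem. It ties the effect size to the difference observed, whereas power is a function of the true difference.

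**Working it through.** **Inputs (Protocol 12.3 and 12.2).** n = 25 per arm; d = difference / SD = 0.5; 1-sided alpha = 0.05; two independent groups, 1:1. Stated power: at least 80%.

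**Power of the planned comparison.**

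- Noncentrality = d × √(n/2) = 0.5 × √12.5 = 1.768.
- Degrees of freedom = 2 × 25 − 2 = 48; 1-sided 5% critical value = 1.677.
- Power = P(T > 1.677), with T noncentral t on 48 df and noncentrality 1.768, = **0.539**.
- Normal approximation: Φ(1.768 − 1.645) = Φ(0.123) = 0.549.
- Probability of missing a true 0.5 SD effect = 1 − 0.539 = 0.461.

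**Does another reading reproduce 80%?**

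| Reading | Power (normal) | Power (t) |
|---|---|---|
| Two-sample, 25 per arm, 1-sided 5% (as written) | 54.9% | 53.9% |
| Two-sample, 25 per arm, 2-sided 5% | 42.4% | 41.0% |
| Two-sample, 25 per arm, 1-sided 10% | 68.7% | 68.1% |
| One-sample or paired, n = 25, 1-sided 5% | 80.4% | 78.3% |
| Two-sample, 50 per arm, 1-sided 5% | 80.4% | 79.9% |

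Only the last two rows come near 80%, and neither is this design. The first treats the comparison as within one group; the second takes the total of 50 as the size of each arm. Either slip could explain the figure, and the document does not show which, if either, occurred.

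**What 80% would require.**

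- Normal approximation: n per arm = 2 × (1.645 + 0.842)² / 0.5² = 49.5, so 50.
- By t: 50 per arm gives 79.9% and 51 gives 80.6%, so 51 per arm, 102 in total.
- With 25 per arm: d = 0.703 (normal) or 0.713 (t).

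**Effect of baseline adjustment.** If 0.5 refers to the unadjusted between-patient SD, adjusting for a baseline that correlates r with Visit 6 divides the SD by 1/√(1 − r²), so the effective d is 0.5/√(1 − r²). The protocol gives no r, so a range is shown:

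| Assumed r | Effective d | Power (t) |
|---|---|---|
| 0.50 | 0.577 | 64% |
| 0.70 | 0.700 | 79% |
| 0.72 | 0.720 | 81% |
| 0.80 | 0.833 | 90% |

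The 80% line is crossed at r of about 0.71. If 0.5 already refers to the residual SD, power stays at about 54%.

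**Observed against true difference.** The smallest observed difference that is significant is 1.677 × √(2/25) = 0.474 SD, and an observed 0.5 SD gives 1-sided p = 0.042. The assumed effect thus lies just above the critical value, as power only slightly above one half implies. The same 0.474 SD is the half-width of the 90% confidence interval, in units of the SD used.

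**Loss of scans.** Section 5.2 says that "Patients who discontinue the study after randomisation will not be replaced", and Section 5.8.1 exempts patients with less than two months of treatment from the second scan. The protocol gives no expected loss. If 22 or 20 per arm had both scans (an assumption), power would be 49% or 46%.

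**The case against.** The best defence is baseline adjustment. The analysis is a covariance model, Section 12.3 does not say which SD it means, and Section 1.3 describes CT airway measurement as accurate and reproducible. With the raw SD and a correlation of about 0.71 or more, 80% is attainable. This stands as a possibility, but the protocol states no such correlation and says it lacks adequate data for a power calculation, so it does not support its own figure.

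A second defence is that this is a declared feasibility study. Sections 1.4 and 12.3 both disclaim formal powering, the size has other stated grounds (similar asthma studies, low radiation exposure), no decision rule rests on AWT-Pi10 significance, and later imaging studies will draw on other trials as well. All of this is true and limits the practical harm. It does not make an explicit numerical claim correct; it adds a contradiction.

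It is also fair to say that how the figure arose is a guess, that the remark about the observed difference largely restates the power result, and that not replacing dropouts is no error in itself. None of these is needed for the conclusion.

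**Conclusion.** The power statement is wrong as written. From the protocol's own inputs, power is about 54% against at least 80% claimed: a shortfall of about 26 percentage points, and a miss probability of about 46% rather than at most 20% for a true effect of 0.5 SD. Because the protocol assumes an effect of at least 0.5, the 80% has to hold at 0.5, and it does not.

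This rests on a two-sample comparison with all 25 patients per arm evaluable and 0.5 expressed in units of the SD that applies in the analysis. The one route back to 80% within this design needs both the raw-SD reading and a correlation of about 0.71 or more, and neither is stated. Sections 12.3 and 1.4 are also inconsistent with each other on whether the study is powered. Because the claim concerns the primary variable, it must be corrected, although the sample size, endpoint and analysis need not change.

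**What to change.** Keep 50 patients. In Section 12.3:

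1. Replace the power sentence with wording such as: With 25 evaluable patients per arm and a 1-sided 5% test, power is about 54% for a true standardised difference of 0.5 and 80% for about 0.71; the expected half-width of the 90% confidence interval is about 0.47 SD.
2. State which SD is meant, preferably the residual SD after baseline adjustment. If the raw SD is intended, give the assumed correlation between baseline and Visit 6, justify it, and compute the power from it.
3. Refer to the true difference, not the observed one.
4. Remove the statement that the number suffices to detect clinically relevant effects, so that the section agrees with its own opening and with Section 1.4.

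It would also help, though it is not essential, to say that a non-significant result will be interpreted through the 90% confidence interval already planned in Section 12.2 and not taken as absence of effect.

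The cost is a change of protocol wording and a less favourable stated power. No extra patients, scans or radiation are involved.

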# 12.4 Safety Review Committee

An independent SRC has been constituted to review accumulated blinded safety data on an ongoing basis throughout the duration of the study. Where necessary, SRC members may have access to unblinded data however no members of the Study team will have access to unblinded data until after database lock is declared. The SRC are governed by a specific SRC charter.

### **13.1.1** Study Participation Card

At Visit 2, all randomised patients will receive a Study Participation Card in local language, see Table 5.

#### Table 5Study participation card

IMPORTANT MEDICAL INFORMATION	IMPORTANT MEDICAL INFORMATION
Name:	Study code: D0520C00014
Enrolment code:	If you have any queries please contact:
Study code: D0520C00014	Dr.:
This patient participates in a clinical study and is	Nurse:
being treated with AZD9668 twice daily on top	Hospital:
of tiotropium as maintenance medication and a	Phone:
short-acting $\beta_2$ -agonist as reliever medication.	

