To be randomised to the 12-week treatment period a visually acceptable MSCT scan with no clinically relevant abnormal CT findings must have been performed 2 to 7 days before Visit 2. Before the patient has the baseline MSCT scan the laboratory safety results from Visit 1b must be reviewed and considered eligible (refer to exclusion criterion 8). The patient must also show complete morning recordings of daily FEV1 data at least 10 of the last 14 days before Visit 2.

At Visit 2 eligible patients will be randomised to either

- AZD9668, 60 mg twice daily
- placebo to match AZD9668

Two weeks after stopping study medication there will be a follow up visit.

An independent safety review committee will review available safety data, see Section 12.4.

The pharmacogenetic part of the study is described in Appendix D.

Clinical Study Protocol Drug Substance AZD9668 Study Code D0520C00014 Edition Number 1 Date

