#### 3.2.2 Rationale for study design

The study will be randomised, placebo-controlled and double-blind to ensure a robust design and minimise bias, which could compromise the conduct of the study and/or interpretation of the results.

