## 5.4.2 Methods for unblinding the study

Individual treatment codes, indicating the treatment randomisation for each randomised patient, will be available to the investigator(s) or pharmacists at the study centre. All code break envelopes must be kept in a safe but accessible place.

The treatment code should not be broken except in medical emergencies when the appropriate management of the patient requires immediate knowledge of the treatment randomisation. The investigator documents and reports the action to AstraZeneca, without revealing which study treatment the patient received to AstraZeneca staff.

A patient whose randomisation code has been broken will be discontinued from the study (see Section 5.8).

AstraZeneca retains the right to break the code for SAEs that are unexpected and are suspected to be causally related to an investigational product and that potentially require expedited reporting to regulatory authorities. Treatment codes will not be broken for the planned analyses of data until all decisions on the evaluability of the data from each individual patient have been made and documented.

On completion of the study, the monitor will ensure and document the return of the code envelopes and also document the reason for any opened envelope, dated and signed by the principal investigator.

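### The Study Participation Card tells every randomised patient's outside clinicians that the patient is on AZD9668, which is untrue for the placebo arm, and does not say that treatment is blinded

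*Protocol*

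**What the plan says.** Section 13.1.1 of the protocol states that at Visit 2 "all randomised patients will receive a Study Participation Card in local language". Table 5 prints the text. The left column opens with "This patient participates in a clinical study and is", continues with "being treated with AZD9668 twice daily on top" and then "of tiotropium as maintenance medication and a", and ends with the short-acting beta2-agonist as reliever. That is one complete sentence. It names AZD9668 and the two background drugs and nothing else.

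The card also carries a heading marking it as important medical information, the study code, the enrolment code, and blank fields for a doctor, a nurse, a hospital and a telephone number.

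The design sections describe a different treatment situation. Section 3.1 randomises patients to AZD9668 60 mg twice daily or to "placebo to match AZD9668". Section 3.2.2 says that "The study will be randomised, placebo-controlled and double-blind to ensure a robust design and minimise bias". Section 5.4.1 provides placebo tablets that look the same as the active tablets. Section 5.4.2 keeps the treatment codes with the investigator or pharmacist at the study centre and reserves their use for "medical emergencies when the appropriate management of the patient requires immediate knowledge of the treatment randomisation". On numbers, Section 12.3 says: "The sample size is 25 patients in each arm".

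**The concern.** The card is the one trial document that the patient is meant to show to people who have never seen the protocol. The protocol foresees such contacts: Sections 5.6.2 and 6.3.9 provide for emergency room treatment and hospital admission for exacerbations, and Section 5.8 lists liver, QTcB, haemolysis and platelet findings that lead to discontinuation. A clinician outside the site who meets one of these findings and reads the card would take exposure to AZD9668 as established. For a placebo patient that is wrong. For either patient it gives a certainty that the trial does not have while the blind is kept. Nothing on the card says that the treatment is blinded or could be placebo.

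What is at stake is the factual accuracy of a safety document. The trial's estimate of the treatment effect is not affected.

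**Working it through.** No power, alpha or event figure enters this point. The check sets the card text against the design sections, with one proportion.

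1. **Who holds the card.** All randomised patients, in both arms, from Visit 2 (Section 13.1.1). There is one version of the text (Table 5).
2. **What the card asserts.** Treatment with AZD9668, without qualification. The sentence runs without a break from trial participation to the reliever medication, so the missing mention of placebo is not a gap left by redaction or by text extraction.
3. **What the holders receive.** AZD9668 or matching placebo (Sections 3.1 and 5.4.1), 25 patients per arm (Section 12.3).
4. **Share for whom the assertion is untrue.** Placebo share = placebo patients / all randomised patients = 25 / (25 + 25) = 25 / 50 = 50%.
5. **For how long.** Section 5.5.3.1 puts the first dose at Visit 2 and the last at Visit 6, so the 50% figure applies to the 12-week treatment period. After Visit 6 the present tense is out of date in both arms. The protocol does not say how long the card is to be carried.
6. **Whether the text reveals allocation.** The wording is identical in both arms, so the probability of being on active treatment given the card text is the same as without it: 25 / 50. No one is unblinded.
7. **Whether the protocol's own usage explains the wording.** In places the protocol writes AZD9668 as shorthand for the blinded product, for example in the Table 2 row for the morning dose at the clinic and its footnotes, and at the start of Section 6.3.4. Elsewhere it names both products: in Section 5.5.3.1, in the restrictions before spirometry in Section 6.3.4, and in the analysis sets in Sections 12.1.1 and 12.1.2. A reader of the whole protocol can decode the shorthand. A reader of the card alone cannot, because the words placebo, blinded and investigational product do not appear on it.

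**The case against.** The strongest reply is that this is a drafting slip with little consequence. The card does disclose trial participation, and it gives codes and a site contact. Section 5.4.2 places the treatment codes at that same site, so an outside clinician has a route to the person who holds them. Within the trial, causality is judged by the investigator (Section 6.4.3), who knows that the study is blinded, and no trial decision depends on the card's wording. All of this stands, and it limits the point. It does not make the sentence true for a placebo patient.

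Four stronger readings are tempting, and the documents do not support them.

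- *A reader might infer that the card conceals the blinding from emergency staff.* It omits the blinding, but the disclosed participation and the contact fields leave a clear way to ask.
- *A reader might infer a contradiction with the code-break rule in Section 5.4.2.* That section governs who may open the code and when. The card changes neither. The conflict is with the existence of a placebo arm and with blinded treatment.
- *A reader might infer that telling patients they are on active drug raises expectation and affects the SGRQ-C, BCSS, EXACT and reliever use.* The protocol gives no basis for sizing such an effect. Section 8.4 requires full information about the nature of the study before consent, and the same text in both arms would not favour either one. The primary variable, AWT-Pi10, is measured by CT.
- *A reader might infer that the false statement applies through follow-up.* The placebo-specific error is confined to the period when tablets are taken.

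One limit remains. The text of Section 13.1 on medical emergencies, which stands just before the card, is not in the copy reviewed. It may tell sites more about emergencies, but it cannot alter the wording printed in Table 5.

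**Conclusion.** The point holds as an error of fact in a patient-carried safety document. The card states active treatment for every holder, and this is untrue for 25 of 50 planned patients (50%) during the 12 weeks of treatment. The figure assumes that randomisation ends close to the planned equal split of about 50 patients.

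The benefit of correcting it is that clinicians outside the site would know that exposure is uncertain. How often the wording would mislead one of them cannot be estimated from the protocol. The error has no consequence for the analysis. The point is minor but worth correcting.

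**What to change.** Reconcile the Table 5 wording with Sections 3.1 and 5.4. The card could read: *This patient is taking part in a double-blind clinical study and is receiving AZD9668 or placebo twice daily, in addition to tiotropium as maintenance medication and a short-acting beta2-agonist as reliever medication. In a medical emergency, please call the study contact given on this card.*

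No dose needs to be added, because the defect does not concern dose. Directing the reader to the site contact is consistent with Section 5.4.2 and leaves the decision on a code break where the protocol puts it. It also avoids inviting code breaks on the card itself. That matters because Section 5.4.2 discontinues any patient whose code is broken, and there are only 25 patients per arm.

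The cost is small but not nil. The card is issued in local languages, so existing translations would have to be revised. Section 8.3 has the Ethics Committee approve written materials given to patients, so a card that has already been submitted may need approval again. The protocol does not say whether either step has been taken. Nothing in the design, the treatment or the analysis changes.
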